15. An abnormal electrocardiogram (ECG) at screening interpreted as 'Abnormal, Significant'. Inclusion of participants with 'Abnormal, Insignificant' ECGs will be based on the principal investigator's discretion.
16. Have an active malignancy or history of metastatic or hematologic malignancy.

AV7909 Anthrax Vaccine

IND 014451

Protocol EBS.AVA.210, Version 3.0 (28 October 2019)

17. Have a history of an autoimmune, inflammatory, vasculitic or rheumatic or rheumatic disease including but not limited to systemic lupus erythematosus, Guillain-Barré syndrome, myasthenia gravis, polymyalgia rheumatica, diabetes mellitus type I, rheumatoid arthritis or scleroderma.
18. A positive laboratory evidence of hepatitis B, hepatitis C, or human immunodeficiency virus (HIV) HIV-1 or HIV-2 infection.
19. Positive result on urine drug screen, any evidence of ongoing drug abuse or dependence (including alcohol), or recent history (over the past five years) of treatment for alcohol or drug abuse.
20. Has an acute disease at the time of enrollment.

Note that screening lab tests may be delayed to allow the resolution of a transient acute condition or the subject may be rescreened according to procedures under [Section 5.4](#).

21. Any medical condition that, in the opinion of the investigator, could adversely impact the participant's involvement or the conduct of the study.
22. Have a significant chronic condition (see Sponsor's guidance on significant chronic conditions in [Appendix C](#)), eg, serious cardiovascular, pulmonary, hepatic, type II diabetes mellitus or renal disease that, in the opinion of the investigator, would render treatment unsafe or would interfere with trial evaluations or completion of the study.
23. An opinion of the investigator that it would be unwise to allow the participant to be randomized into the study.
24. Member or immediate family member of an investigator site team.

Investigational Products (IP), Dosage, Schedule and Mode of Administration:

- AV7909 (containing 0.5 mL AVA + 0.25 mg CPG 7909 adjuvant per dose) will be administered IM in the deltoid muscle of alternating arms to all (Groups 1 to 3) on Day 8 and Day 23.
- Ciprofloxacin (500 mg po q 12 hr) will be administered to participants in Group 1 on Days 4-9, Days 22-24, and Days 31-37.
- Doxycycline (100 mg po q 12 hr) will be administered to participants in Group 2 on Days 2-9, Days 22-24, and Days 32-38.

Duration of Treatment:

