Independent safety oversight will be provided by a Data Safety Monitoring Board (DSMB), which will be notified of significant AEs (refer to [Section 8.5](#)) as determined by the medical monitor (MM) on an ongoing basis. The DSMB will comprise at least three voting members, to include one expert in immunology to specifically support the evaluation of potential AESIs for autoimmune etiology, if pre-existing or new onset, and relationship to the study product. The DSMB will make recommendations regarding the safety of continuing enrollment and dosing. Study enrollment and dosing may be interrupted at the request of the DSMB Chair if it is believed that an AE represents a significant safety concern requiring suspension of dosing pending full DSMB evaluation. The operations of the DSMB will be detailed in a DSMB Charter.

AV7909 Anthrax Vaccine
 IND 014451
 Protocol EBS.AVA.210, Version 3.0 (28 Oct 2019)

Figure 1: Study Design for EBS.AVA.210

cipro = ciprofloxacin; doxy = doxycycline; PK = pharmacokinetics; po = per os, (oral); q12 h = every 12 hours; TNA = toxin-neutralizing antibody; TSH = thyroid-stimulating hormone

^aIn Group 1, the evening dose on Day 37 is not administered ^bAntibiotic dosing for Groups 1 & 2 up to Day 8 is to enable 2 PK sessions prior to vaccination #1 (vac #1) on Day 8. Dosing continues on Day 9, extends around vac #2 (on Days 22 to 24) and then discontinues until Day 31 (cipro) or Day 32 (doxy). Cipro dosing continues from Day 31 to Day 37 and doxy dosing continues from Day 32 to Day 38, encompassing 2 PK sessions after the complete vaccination regimen as well as the blood draw for TNA. ^cSolid lines at Days 1, 8, 23, 37 and 51 are days when all groups have in-clinic visits. Days in red are those when Groups 1A and/or 2A have clinic visits for blood draws for pre-dose, trough values or PK.

[figure not shown]

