6.1.3. Doxycycline Description

Doxycycline hyclate, USP, is a broad-spectrum antibiotic synthetically derived from oxytetracycline. The chemical designation is 4-(Dimethylamino)-1,4,4a,5,5a,6,11,12a-octahydro-3,5,10,12,12a-pentahydroxy-6-methyl-1,11-dioxo-2-naphthacene-carboxamide monohydrochloride, compound with ethyl alcohol (2:1), monohydrate. Doxycycline is a light-yellow crystalline powder. The hyclate has a molecular weight 1025.9 with an empiric formula of $(C_{22}H_{24}N_2O_8 \cdot HCl)_2 \cdot C_2H_6O \cdot H_2O$.

Doxycycline will be provided as tablets of doxycycline hyclate at strength of 100 mg doxycycline equivalent. The manufacturer and exact formulation, ie, excipients, and format for the tablets will be specified in the Pharmacy Manual.

AV7909 Anthrax Vaccine

IND 014451

Protocol EBS.AVA.210, Version 3.0 (28 October 2019)

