6.1.6. Administration of Doxycycline

Doxycycline (100 mg po q 12 hr) will be administered only to participants in Group 2. A total of 35 ± 2 doses will be administered in three courses as shown in [Figure 2](#).

Group 2A participants will nominally receive 20 of their 35 doxycycline doses in the clinic whereas Group 2B will nominally receive two of their 35 doxycycline doses in the clinic. The remaining doses will be taken at home. Doses should be taken at the same times \pm 30 min each day. Doses administered in the clinic will be recorded by the staff with the date and time of administration in each participant's source documents and eCRF. Doses self-administered at home will be recorded by the participant with the time of administration in their e-diary. Refer to [Section 8.3.5.1](#) for additional details on the e-diary. If a participant misses a dose, they should be instructed to take the dose as soon as remembered, but no later than 4 hours of its scheduled time. The participant should then wait until the next scheduled dose. The participant should not take two doses at the same time.

Exact details regarding the format in which the doses will be provided to the participants will be provided in the Pharmacy Manual.

Certain foods and over-the-counter products can interfere with the absorption of doxycycline so prior to administration of doses in the clinic, site staff should ask each participant if they have eaten certain dairy products (such as milk or yogurt) or taken magnesium/aluminum antacids, other highly buffered drugs, or other products containing calcium, iron or zinc since their last dose and if so record this information along with the timing of intake (eg, 6 hours since their last dose). This information along with other precautions that need to be followed when taking doxycycline will be provided to participants when they are given their supplies of doxycycline for self-administration (see [Section 5.3.1](#)).

AV7909 Anthrax Vaccine

IND 014451

Protocol EBS.AVA.210, Version 3.0 (28 October 2019)

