8.1.3.2. Group 1B: Day 8 – Vaccination #1

1. Review eligibility.
2. Staff will review the ciprofloxacin supply and review the e-diary entries, conducting a compliance check of the remaining doses compared to the e-diary record. Staff will record ciprofloxacin doses to document compliance. Staff will also discuss any changes in the use of concomitant medication while reminding the participant of the precautions in Section 5.3.
3. Review and record AEs.
4. Conduct a symptom-directed PE, if required.
5. Assess vital signs (seated/semi-recumbent blood pressure, heart rate, respiratory rate and temperature).
6. For WOCBP, collect and perform UPT (prior to AV7909 vaccination). Positive UPTs will be confirmed with a serum pregnancy test. All confirmed pregnancies in participants who receive at least one dose of AV7909 or ciprofloxacin and where conception occurs prior to 12 months after last receipt of either IP will be followed to outcome.

AV7909 Anthrax Vaccine

IND 014451

Protocol EBS.AVA.210, Version 3.0 (28 October 2019)

7. Administer ciprofloxacin 500 mg po in AM prior to vaccination; the evening dose of ciprofloxacin 500 mg po will be self-administered at home 12 hours after the AM dose [and at approximately the same time (± 30 min) each day].
8. Administer AV7909 vaccination #1. Participants should be monitored for at least 30 minutes following vaccine administration for any adverse effects especially anaphylaxis.
9. Assess vital signs at 30 ± 5 min postvaccination.
10. Prior to being discharged from the clinic, the participant will be given and trained on an e-diary to capture local and systemic reactogenicity events (ie, reactogenicity e-diary) and to record daily for at least seven days following each vaccination. If a reaction is not resolved at seven days postvaccination, the participant is to continue completing the e-diary daily until they are symptom free for two consecutive days. Participants will be given an injection site reaction measurement tool and shown how to use it to measure the size and assess the severity of certain reactogenicity events associated with vaccination. See [Section 8.3.5.1](#) (e-diary) and remind participants about the diet and activity precautions that must be followed when taking ciprofloxacin (see [Section 5.3](#)).

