8.1.5.2. Group 2B: Day 8 – Vaccination #1

1. Review eligibility.
2. Staff will review the doxycycline supply and review the e-diary entries, conducting a compliance check of the remaining doses compared to the e-diary record. Staff will also discuss any changes in the use of concomitant medication.
3. Review and record AEs.
4. Conduct a symptom-directed PE, if required.
5. Assess vital signs (seated/semi-recumbent blood pressure, heart rate, respiratory rate and temperature).
6. For WOCBP, collect and perform UPT (prior to AV7909 vaccination). Positive UPTs will be confirmed with a serum pregnancy test. All confirmed pregnancies in participants who receive at least one dose of AV7909 or doxycycline and where conception occurs prior to 12 months after last receipt of either IP will be followed to outcome.

AV7909 Anthrax Vaccine

IND 014451

Protocol EBS.AVA.210, Version 3.0 (28 October 2019)

7. Administer doxycycline 500 mg po in AM prior to vaccination; the evening dose of doxycycline 100 mg po will be self-administered at home 12 hours after the AM dose [and at approximately the same time (± 30 min) each day].
8. Administer AV7909 vaccination #1. Participants should be monitored for at least 30 minutes following vaccine administration for any adverse effects especially anaphylaxis.
9. Assess vital signs at 30 ± 5 minutes post-vaccination.
10. Prior to discharge from the clinic, the participant will be given and trained on an e-diary to capture local and systemic reactogenicity events (ie, reactogenicity e-diary) and to record daily for at least seven days following each vaccination. If a reaction is not resolved at seven days postvaccination, the participant is to continue completing the e-diary daily until they are symptom free for two consecutive days. Participants will be given an injection site reaction measurement tool and shown how to use it to measure the size and assess the severity of certain reactogenicity events associated with vaccination. See [Section 8.3.5.1](#) (e-diary) and remind participants about the diet and activity precautions that must be followed when taking doxycycline (see [Section 5.3](#)).

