8.1.5.4. Group 2B: Day 23 (± 1 day) – Vaccination #2

1. Staff will review the participant's doxycycline supply and review e-diary entries, conducting a compliance check of the remaining doses compared to the e-diary record. Staff will also discuss any changes in the use of concomitant medication as well as any vaccination reactions if still ongoing, and reminding the participant of the precautions in [Section 5.3](#).
2. Review and record AEs.
3. Perform symptom-directed PE, if required.
4. Record concomitant medications.
5. Assess vital signs (seated/semi-recumbent blood pressure, heart rate, respiratory rate, and temperature).

AV7909 Anthrax Vaccine

IND 014451

Protocol EBS.AVA.210, Version 3.0 (28 October 2019)

6. Review eligibility for continuing vaccination.
7. For WOCBP, collect and perform UPT (prior to AV7909 vaccination). Positive UPTs will be confirmed with a serum pregnancy test. All confirmed pregnancies in participants who receive at least one dose of any IP and where conception occurs prior to 12 months after last receipt of any IP will be followed to outcome.
8. Administer doxycycline 100 mg po in AM; the evening dose will be self-administered at home.
9. Administer AV7909 vaccination #2; this should occur after doxycycline dosing. Participants should be monitored for at least 30 minutes following vaccine administration for any adverse effects especially anaphylaxis.
10. Following the 30 (\pm 5) minutes of observation, repeat vital signs (seated/semi-recumbent blood pressure, heart rate, respiratory rate, and temperature) measurement.
11. After diary review, participants will be reminded to continue to use the reactogenicity e-diary and injection site reaction measurement tool, to capture any use of concomitant medications and to record the dates and times they self-administer their doxycycline doses on the antibiotic e-diary. See [Section 8.3.5.1](#).
12. Prior to discharge on Day 23, participants doxycycline supply will be returned, and participants will be reminded to return to clinic in two weeks (\pm 1 day) on Day 37 \pm 1d for the final blood draws for TNA. Again, participants are to continue dosing with doxycycline through the morning of Day 37.

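### Protocol Section 8.1.5.2 item 7 tells staff to give Group 2B 500 mg of doxycycline on the morning of Day 8, five times the intended 100 mg

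*Protocol*

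**What the plan says.** Item 7 of Protocol Section 8.1.5.2 (Group 2B, Day 8) reads: "Administer doxycycline 500 mg po in AM prior to vaccination; the evening dose of doxycycline 100 mg po will be self-administered at home". Item 8 of the same list is the first AV7909 vaccination.

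The regimen in the synopsis, which covers Day 8, is: "Doxycycline (100 mg po q 12 hr) will be administered to participants in Group 2 on Days 2-9, Days 22-24, and Days 32-38". The product description in Section 6.1.3 states: "Doxycycline will be provided as tablets of doxycycline hyclate at strength of 100 mg doxycycline equivalent". Section 6.1.6 repeats 100 mg every 12 hours, sets the course with "A total of 35 ± 2 doses will be administered in three courses", and adds that "Group 2B will nominally receive two of their 35 doxycycline doses in the clinic". Those two doses are Day 8 morning and Day 23 morning. For Day 23, Section 8.1.5.4 item 8 reads: "Administer doxycycline 100 mg po in AM; the evening dose will be self-administered at home".

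The matching ciprofloxacin step for Group 1B, Section 8.1.3.2 item 7, reads: "Administer ciprofloxacin 500 mg po in AM prior to vaccination; the evening dose of ciprofloxacin 500 mg po will be self-administered at home".

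**The concern.** This is a dosing order in current Version 3.0 text, carried out by site staff, and it contradicts the regimen. A nurse working down the Day 8 list would meet 500 mg at the point of administration. The site cannot comply with both this item and Section 6.1.6. Section 11.6 allows staff to depart from the protocol only to remove an immediate hazard, and Section 14 leaves changes to the sponsor.

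The participants are healthy volunteers, and Section 4.2 says intermittent dosing was chosen to limit their antibiotic exposure. The dose falls immediately before vaccination 1, so any ill effect would arise in the post-vaccination observation period. That would complicate the separate attribution to antibiotic and vaccine that Section 9.2.2 asks for. It would also change antibiotic exposure at vaccination 1 in part of the Group 2 arm of the immunogenicity comparison.

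**Working it through.** No sample size, power or alpha figure is involved. The check is a comparison of texts followed by dose arithmetic.

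**Where a doxycycline dose is stated**

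| Place | Dose |
|---|---|
| Protocol synopsis | 100 mg every 12 h |
| Protocol 4.1.3 (Group 2A schedule) and 4.3.3 (dose justification) | 100 mg twice daily |
| Protocol 6.1.3 (tablet strength) | 100 mg |
| Protocol 6.1.6 | 100 mg every 12 h |
| Protocol 8.1.4.2, 8.1.4.5, 8.1.4.9, 8.1.4.11 to 8.1.4.13 (Group 2A visits) | 100 mg |
| Protocol Table 8, footnote n (Group 2B) | 100 mg every 12 h |
| Protocol 8.1.5.1, 8.1.5.3 to 8.1.5.6 (Group 2B, other days) | 100 mg |
| SAP 2.2.1 | 100 mg every 12 h |
| **Protocol 8.1.5.2 item 7, morning dose** | **500 mg** |
| Protocol 8.1.5.2 item 7, evening dose | 100 mg |

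Some items name no dose, for example the Group 2A Day 7 evening dose and the Day 23 morning dose in Section 8.1.4.7. Section 4.1.4 also gives no milligram figure, but says Group 2B is treated as Group 2A apart from the PK and trough visits. None of these supports 500 mg.

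**Likely source.** Items 7 of Sections 8.1.3.2 and 8.1.5.2 are the same sentence with the drug name changed. The ciprofloxacin version has 500 mg morning and evening. In the doxycycline version only the evening figure is 100 mg.

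**Number of doses.** Days 2–9 give 8 × 2 = 16, Days 22–24 give 3 × 2 = 6, and Day 32 to Day 38 morning gives 6 × 2 + 1 = 13. The total is 16 + 6 + 13 = 35, which reproduces the protocol's figure.

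**Size if item 7 is followed**

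- Single dose: 500 / 100 = 5 times, or five tablets instead of one.
- Day 8 total: 500 + 100 = 600 mg against 2 × 100 = 200 mg, or 3 times.
- Nominal course: 34 × 100 + 500 = 3,900 mg against 35 × 100 = 3,500 mg; 3,900 / 3,500 = 1.114, or +11.4%.
- Participants: up to 30 of 70 in the doxycycline arm, 30 / 70 = 43%.
- Compliance under SAP Section 5.4.1 (tablets taken over tablets required): (34 + 5) / 35 = 39 / 35 = 111%. Extra tablets cannot push anyone below the 50% rule for the Immunogenicity Population.

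**Minor inconsistency in the same group's schedule.** The end of the third course differs by section:

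- Sections 8.1.5.4 item 12 and 8.1.5.6 stop on the morning of Day 37 (for a Day 37 draw): 16 + 6 + 11 = 33.
- Section 8.1.5.5 runs through Day 37: 16 + 6 + 12 = 34.
- The 35-dose count ends on the morning of Day 38.
- Table 8, read literally with both doses on every at-home day from 32 to 38: 16 + 6 + 14 = 36.

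All four lie within 35 ± 2, that is 33 to 37. With a Day 37 draw, only doses after the TNA sample are in question.

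**The case against.** The strongest reply is that nobody would carry this out. The same sentence gives 100 mg for the evening, Section 6.1.6 and Table 8 footnote n say 100 mg, and the tablets are 100 mg, so staff would have to hand over five where neighbouring steps use one. Supplies are also checked against the e-diary at that visit. The documents contain no data on harm from a single 500 mg dose, so any injury is potential rather than shown.

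Much of this stands. Execution is unlikely, and no specific toxicity can be claimed from the documents. But these safeguards lower the chance of error without correcting the order. Five tablets is a feasible instruction. The supply check in item 2 comes before the dose in item 7, so it would not catch it. Footnote n also sends the reader to Section 6.1.4, which covers AV7909 administration; doxycycline is in Section 6.1.6.

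The objection is also fair on the secondary points. The Day 37/38 differences are editorial. The third-course reminder in Section 8.1.5.5, keyed to Day 31, can be read as fitting a Day 32 start.

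**Conclusion.** The concern holds. Section 8.1.5.2 item 7 contains a drafting error in an operative dosing step: 500 mg where 100 mg is meant. If followed, it gives five times the intended dose once, three times the intended Day 8 total, and 11% more over the course, in up to 30 participants. This must be fixed, because the instruction concerns participant dosing and costs almost nothing to correct.

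The sizes rest on the planned Group 2B size of 30 and the nominal 35-dose course. The Pharmacy Manual was not available, so whether it repeats or corrects the figure is unknown. The carry-over from ciprofloxacin is an inference from the matching wording. The primary PK endpoints are unaffected.

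**What to change.** 1. In Section 8.1.5.2 item 7, change the morning doxycycline dose from 500 mg to 100 mg.
2. Notify all sites at once. Section 14 lets the sponsor implement a change that removes an apparent immediate hazard without waiting for IRB approval, with notification within 5 working days.
3. Check that the Pharmacy Manual does not carry the 500 mg figure.
4. If any Group 2B participant has passed Day 8, check the recorded dose and tablet count, and handle any 500 mg dose as a dosing-error deviation under Section 11.6.
5. In the same clarification, point Table 8 footnote n to Section 6.1.6. Align Sections 8.1.5.4 item 12, 8.1.5.5 and 8.1.5.6 with the 35-dose schedule: stop after Day 24, restart on Day 32, last dose on the morning of Day 38. The Figure 1 note already says that dosing stops after the second course "and then discontinues until Day 31 (cipro) or Day 32 (doxy"). Key the third-course reminder to Day 32.

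The essential change is one number and a site memo. Item 5 is wording only. No visits, procedures or analyses are added.

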8.1.5.3. Group 2B: Days 9, 22 and 24 (At home)

On Days 9, 22 and 24, the participant is to self-administer doxycycline (100 mg po q 12 hr) at home (at about the same times [± 30 min) each day]). The participant will continue with the e-diary as described in [Section 8.3.5.1](#).

It is required that participants self-administer doxycycline on the day before (morning and evening, the day of (evening), and the day after vaccination (morning and evening). The site must contact the participant to remind them to begin their second course of the antibiotics (ie, the site should contact the participant within 24 hours of the anticipated start day for the second course of antibiotics in relation to the scheduled second vaccination date). Any participant who schedules vaccination 2 (on Day 23) to shift within the allowable window (± 1 days) will be reminded to start their doxycycline dosing on the appropriate day, eg, if the second vaccination shifts to Day 22 then the participant will be reminded to start taking doxycycline on the morning and evening of Day 21 in order to meet the dosing requirement.

8.1.5.4. Group 2B: Day 23 (± 1 day) – Vaccination #2

1. Staff will review the participant's doxycycline supply and review e-diary entries, conducting a compliance check of the remaining doses compared to the e-diary record. Staff will also discuss any changes in the use of concomitant medication as well as any vaccination reactions if still ongoing, and reminding the participant of the precautions in [Section 5.3](#).
2. Review and record AEs.
3. Perform symptom-directed PE, if required.
4. Record concomitant medications.
5. Assess vital signs (seated/semi-recumbent blood pressure, heart rate, respiratory rate, and temperature).

AV7909 Anthrax Vaccine

IND 014451

Protocol EBS.AVA.210, Version 3.0 (28 October 2019)

6. Review eligibility for continuing vaccination.
7. For WOCBP, collect and perform UPT (prior to AV7909 vaccination). Positive UPTs will be confirmed with a serum pregnancy test. All confirmed pregnancies in participants who receive at least one dose of any IP and where conception occurs prior to 12 months after last receipt of any IP will be followed to outcome.
8. Administer doxycycline 100 mg po in AM; the evening dose will be self-administered at home.
9. Administer AV7909 vaccination #2; this should occur after doxycycline dosing. Participants should be monitored for at least 30 minutes following vaccine administration for any adverse effects especially anaphylaxis.
10. Following the 30 (\pm 5) minutes of observation, repeat vital signs (seated/semi-recumbent blood pressure, heart rate, respiratory rate, and temperature) measurement.
11. After diary review, participants will be reminded to continue to use the reactogenicity e-diary and injection site reaction measurement tool, to capture any use of concomitant medications and to record the dates and times they self-administer their doxycycline doses on the antibiotic e-diary. See [Section 8.3.5.1](#).
12. Prior to discharge on Day 23, participants doxycycline supply will be returned, and participants will be reminded to return to clinic in two weeks (\pm 1 day) on Day 37 \pm 1d for the final blood draws for TNA. Again, participants are to continue dosing with doxycycline through the morning of Day 37.

